**Geometric Mean Ratio (GMR)**

GMRs measure the changes in immunogenicity titers/concentrations *within* participants.

The GMR will be calculated using the following formula:

$$10^{\left(\frac{\sum_{i=1}^{n_g} \log_{10}\left(\frac{v_{ij}}{v_{ik}}\right)}{n_g}\right)} = 10^{\left(\frac{\sum_{i=1}^{n_g} \log_{10}(v_{ij}) - \log_{10}(v_{ik})}{n_g}\right)}$$

where, for  $n_g$  participants in vaccine groups  $g = 1$  and  $2$ ,  $v_{ij}$  and  $v_{ik}$  are observed immunogenicity titers/concentrations for participant  $i$  at time-points  $j$  and  $k$ ,  $j \neq k$ .

**4-fold rise**

For the serogroups A, C, W, Y and for each of the serogroup B indicator strains evaluation the 4-fold rise is defined as:

- a post-vaccination hSBA titer  $\geq 16$  for participants with a pre-vaccination hSBA titer  $< 4$ ;
- a post-vaccination hSBA titer  $\geq 4$  times the LLOQ for participants with a pre vaccination hSBA titer  $\geq$  limit of detection (LOD) but  $< \text{LLOQ}$ ; and,
- a post-vaccination hSBA titer  $\geq 4$  times the pre-vaccination titer for participants with a pre-vaccination hSBA titer  $\geq \text{LLOQ}$ .

Document: C:\ProgramData\activePDF\Temp\DocConverter\API\input\99638a57dafd\$76D9DDEF7D8D4E7C B4DEE6C228977964.docx

Author: PPD

Version Number: Final 5.0

**CONFIDENTIAL** Version Date: 05SEP2022

## 6.7. SOFTWARE VERSION

All analyses will be conducted using SAS version 9.4 or higher.

## 7. STATISTICAL CONSIDERATIONS

### 7.1. ADJUSTMENTS FOR COVARIATES AND FACTORS TO BE INCLUDED IN ANALYSES

The following covariates and factors will be used in the analyses in addition to the vaccine group. For details of their inclusion in the models, see the specific analysis subsections in Section 16.

- Baseline titers as a covariate in the Analysis of Covariance (ANCOVA) models
- Country as a factor in the Analysis of Variance (ANOVA) and ANCOVA models.

### 7.2. MULTICENTER STUDIES

This study will be conducted by multiple investigators at multiple centers in approximately 4 countries. Randomization to vaccine group will be minimized by country. Additional analyses by country may be conducted as deemed necessary.

For continuous endpoints (GMT/GMR), the vaccine group effects will be investigated using a linear model that includes a factor for country differences but will not consider vaccine-by-country interaction, i.e., the model only considers effects for country and vaccine. If the statistical model does not converge due to the factor “country”, a model without country effect will be fitted instead. If significant vaccine effects are found in a trial, there will be an exploration of the heterogeneity of vaccine group effects across countries. Results of vaccine by country interaction analysis will be provided in Appendix 16.1.9 of the Clinical Study Report (CSR).

### 7.3. MISSING DATA

---

Document: C:\ProgramData\activePDF\Temp\DocConverter\API\input\99638a57dafd\$76D9DDEF7D8D4E7C  
B4DEE6C228977964.docx

Author: PPD

Version Number:

Final 5.0

**CONFIDENTIAL**

Version Date:

05SEP2022

There will only be limited imputation of missing data. To minimize the effect of dropouts and missing data, the study period will be divided into time intervals for statistical analysis of safety.

#### **Unsolicited Adverse Events Missing or Partial Dates**

Missing and partial AE start dates will be imputed as described in APPENDIX 2, only to determine the relationship between the start date of the event and the first dose date of vaccination. Partial dates will be presented as recorded in the data listings.

#### **Missing intensity and relatedness for unsolicited AEs**

Missing severity, relationship with study vaccine, and outcome of unsolicited adverse events will not be replaced and will appear as 'UNKNOWN' in all statistical output.

#### **Missing Solicited Event Measurements**

On the solicited events eDiary, participants are instructed to enter a measurement for solicited administration site events (i.e., injection site pain, erythema, swelling, induration) and solicited systemic events (i.e., fever [body temperature  $\geq 38.0^{\circ}\text{C}/100.4^{\circ}\text{F}$ ], nausea, fatigue, myalgia, arthralgia, headache) during the 7 days (including the day of vaccination) following vaccination at Day 1, Month 0 and Day 181, Month 6.

#### **Titers Measured Below (or Above) the LLOQ (or ULOQ)**

For the hSBA assay, a titer value measured below LLOQ will be imputed to a value that equal to LLOQ/2 in summaries and analyses but will be listed as reported in the raw serology data. For example, a serologic assay with LLOQ = 30 generally reports values below LLOQ as "<30". The data listings will present the values as "<30", while values of 15 are to be used in the summaries and analyses.

Titer values measured as above ULOQ will be imputed at the ULOQ value.

Otherwise, missing immunogenicity values are considered Missing Completely at Random (MCAR) and "therefore will not contain information that impact the result of the analysis (i.e., not informative).

Imputation methods will therefore not be used.

## **7.4. MULTIPLE COMPARISONS/ MULTIPLICITY**

---

Document: C:\ProgramData\activePDF\Temp\DocConverter\API\input\99638a57dafd\$76D9DDEF7D8D4E7C  
B4DEE6C228977964.docx

Author: PPD

Version Number: Final 5.0

**CONFIDENTIAL** Version Date: 05SEP2022

For the multiplicity adjustment, all hypotheses will be ranked into two families, family 1 and family 2. Fixed sequential testing with full alpha propagation in these pre-ordered hypotheses families will be applied. Refer protocol section 9.2 sample size determination for more details.

## **7.5. ACTIVE-CONTROL STUDIES INTENDED TO SHOW NON-INFERIORITY**

NI will be demonstrated if, the lower limit of 2-sided 95% confidence interval (CI) for the percent difference in 4-fold rise (refer to Section 6.6) in hSBA titers ( $p_{\text{MenABCWY}} - p_{\text{MenACWY}}$ ) is above -10%, for each N. meningitidis A, C, W, and Y serogroup. Additional details provided in Section 16 of this SAP.

## **7.6. EXAMINATION OF SUBGROUPS**

Subgroup analyses will be conducted for the Primary immunogenicity analyses only. It should be noted that the study was not designed to detect treatment differences with high statistical power within subgroups. The following subgroups will be assessed and described within the immunogenicity analysis sections: Gender (Female, Male), Race (White, Non-white), Age in years (15 to <18,  $\geq 18-25$ ), Country (by country, and 'US vs. Rest of the World (ROW)').

## **7.7. RANDOMIZATION AND BLINDING**

### **7.7.1. METHOD OF GROUP ASSIGNMENT AND RANDOMIZATION**

For further details please refer to Section 6.3 of the protocol.

### **7.7.2. DEFINITION OF RANDOMIZATION/VACCINATION ERRORS**

The list below provides some examples of potential errors that may occur during vaccination:

- Administration of concomitant vaccine(s) forbidden in the protocol (code 1040)
- Randomisation failure (participant not randomized in correct group) (code 1050)
- Randomisation code was broken (code 1060)

---

Document: C:\ProgramData\activePDF\Temp\DocConverter\API\input\99638a57dafd\$76D9DDEF7D8D4E7C  
B4DEE6C228977964.docx

Author: PPD

Version Number:

Final 5.0

**CONFIDENTIAL**

Version Date:

05SEP2022

- Dosing not according to protocol (code 1070)
- Dosing after a Temperature deviation (code 1080)
- Dosing after expiration (code 1090)

Randomization errors will be summarized by presenting the number and percentage of participants with randomization errors for the enrolled set. Participants with randomization errors should be analyzed as randomized in FAS, excluded from PPS and analyzed as received for Safety.

## 8. OUTPUT PRESENTATIONS

Programming Conventions for Outputs shows conventions for presentation of data in outputs.

The templates (table shells) provided with this SAP describe the presentations for this study and therefore the format and content of the summary tables, figures, and data listings to be provided by IQVIA Biostatistics.

Statistical output numbering will follow 'ICH E3 Structure and Content of Clinical Study Reports'.

## 9. DISPOSITION AND WITHDRAWALS

All participants from the ENR Set will be accounted for in this study.

### 9.1. DISPOSITION

The number of enrolled, vaccinated (at least 1 vaccination, full vaccination course), completed participants, screening failures, reason for withdrawal, and reason for exclusion from analysis sets, as well as number of participants in FAS and PPS will be reported by group for the ENR set. Additionally, the number of participants discontinuing the study and the reason for discontinuation, including COVID-19, will be presented.

A data listing of the disposition information will be provided. If applicable, early study discontinuation or withdrawals due to having COVID-19 or COVID-19 related issues will be presented. The number of

---

Document: C:\ProgramData\activePDF\Temp\DocConverter\API\input\99638a57dafd\$76D9DDEF7D8D4E7C  
B4DEE6C228977964.docx

Author: PPD

Version Number: Final 5.0

**CONFIDENTIAL** Version Date: 05SEP2022

participants who discontinued study drug and who withdrew from the Study due to COVID-19 infection or issues related to the COVID-19 pandemic will be presented.

## 9.2. PROTOCOL DEVIATIONS

Protocol deviations will be collected in a PD log, as detailed in the Protocol Deviations Management Plan.

All protocol deviations will be assessed as important or non-important. Protocol deviations will be reviewed by the GSK Team, and their status confirmed by the time that all data are cleaned for the Final Analysis. APPENDIX 3 lists PDs that affect the validity of the immunogenicity measurements and result in exclusion of participants from the PPS.

A summary presenting the number and percentage of participants in each PD category will be presented for participants in the ENR set, by vaccine group and overall, and a data listing will be provided for participants with protocol deviations during the study. Additionally, a data listing of PDs for participants who are excluded from the PPS will be generated.

A summary presenting the number and percentage of participants with a protocol deviation related to COVID-19 in each PD category will be presented for participants in the ENR set, by vaccine group and overall. Additionally, PDs related to COVID-19 will be flagged in the PD listing.

## 10. DEMOGRAPHIC AND OTHER BASELINE CHARACTERISTICS

Demographic data and other baseline characteristics will be presented for the ENR, ES, FAS and PPS. No statistical testing will be carried out for demographic or other baseline characteristics.

The following demographic and other baseline characteristics will be reported for this study: Age (years) at the time of the first vaccination, Sex, Race, Ethnicity, Weight (kg), Height (cm) and Body Mass Index (BMI) ( $\text{kg}/\text{m}^2$ ). Descriptive statistics (mean, standard deviation [SD], median, minimum and maximum) for age, height, weight, and body mass index will be calculated overall and by vaccine group. Distributions of participants by sex, race, and ethnic origin will be summarized overall and by vaccine group.

---

Document: C:\ProgramData\activePDF\Temp\DocConverter\API\input\99638a57dafd\$76D9DDEF7D8D4E7C  
B4DEE6C228977964.docx

Author: PPD

Version Number: Final 5.0

**CONFIDENTIAL** Version Date: 05SEP2022

## 10.1. DERIVATIONS

### Age (years) at first vaccination

When age at vaccination is to be displayed in years, it will be calculated as the number of complete calendar years between the date of birth and the date of vaccination. For example:

- DOB = 10SEP1983, Date of vaccination = 09SEP2018 -> Age = 34 years
- DOB = 10SEP1983, Date of vaccination = 10SEP2018 -> Age = 35 years

Note: If we have partial DOB, the DOB will be imputed as described in APPENDIX 2.

### Weight

Weight will be presented in kilograms. Weights reported in pounds will be converted as follows:

- Weight in kilograms = Weight in pounds / 2.2

### Height

Height will be presented in centimeters. Heights reported in feet and inches will be converted as follows:

- Height in centimeters = Height in inches x 2.54

### Body mass index (BMI)

BMI will be calculated as follows:

- $BMI (kg/m^2) = (Weight \text{ in kilograms}) / (Height \text{ in meters})^2$

### Temperature

Temperatures will be presented in degrees Celsius (°C). Temperatures reported in degrees Fahrenheit (°F) will be converted as follows:

- $Temperature (Celsius) = ((Temperature (Fahrenheit) - 32) \times 5) / 9$

## 11. VACCINATION AND MEDICAL HISTORY

Vaccination and Medical History information will be presented for the ES.

---

Document: C:\ProgramData\activePDF\Temp\DocConverter\API\input\99638a57dafd\$76D9DDEF7D8D4E7C  
B4DEE6C228977964.docx

Author: PPD

Version Number:

Final 5.0

**CONFIDENTIAL** Version Date:

05SEP2022

- Vaccination History:
  - Identity of the primary MenACWY vaccination
  - Age at primary MenACWY vaccination.
- Medical History will be coded using the current version of the Medical Dictionary for Regulatory Activities (MedDRA):
  - Medical History conditions are defined as those conditions which stop prior to or at the first vaccination.
  - Presented by System Organ Class (SOC) and Preferred term (PT).

## 12. CONCOMITANT ILLNESSES

Concomitant Illnesses (also captured on the Medical History page) will be presented for the ES.

- Concomitant Illnesses will be coded using the current version of the MedDRA dictionary:
  - Concomitant Illnesses are conditions which started prior to the first vaccination and are ongoing at the first vaccination.
  - Presented by SOC and PT.

## 13. MEDICATIONS

Medications will be presented for the ES and coded using the current version of World Health Organization (WHO) Drug dictionary. Medications will be presented by anatomical therapeutic chemical (ATC) classification and preferred drug name, overall and by vaccine group.

See APPENDIX 2 for handling of partial dates for medications, in the case where it is not possible to define a medication as prior or concomitant, the medication will be classified by the worst case; i.e. concomitant.

- ‘Prior’ medications are medications which started and stopped prior to the first vaccination.
- ‘Concomitant’ medications are medications which:
  - started prior to, on or after the first vaccination, AND

---

Document: C:\ProgramData\activePDF\Temp\DocConverter\API\input\99638a57dafd\$76D9DDEF7D8D4E7C  
B4DEE6C228977964.docx

Author: PPD

Version Number:

Final 5.0

**CONFIDENTIAL**

Version Date:

05SEP2022

- ended on or after the date of first vaccination or were ongoing at the end of the study.

## 14. STUDY MEDICATION EXPOSURE

The total time in the study (including follow-up after the last vaccination) will be summarized as a continuous variable by vaccine group and overall. The total time in study is defined as the number of days from the first vaccination to the date of last contact specified on the End of Study Visits form. This will generally be the date of the last telephone contact (scheduled on Day 361). The vaccination date/time information will be listed for each participant.

### 14.1. DERIVATIONS

Total time in study (days) = date of last contact – date of first vaccination + 1.

## 15. STUDY MEDICATION COMPLIANCE

Compliance to study medication will be presented for the ES.

The number and percentage of participants receiving 1 dose, 2 doses or all 3 doses will be presented overall and by vaccine group for the ES. For each intervention, the number of participants receiving the vaccine outside the specified window will be presented.

The number and percentage of participants who missed each dose or received the dose outside the planned window due to COVID-19 will be presented (if applicable) overall and by vaccine group for the ES.

## 16. IMMUNOGENICITY OUTCOMES

### 16.1. PRIMARY IMMUNOGENICITY

#### 16.1.1. PRIMARY IMMUNOGENICITY VARIABLE & DERIVATIONS

The first co-primary immunogenicity variable is the percentages of participants with a 4-fold rise (refer to

---

Document: C:\ProgramData\activePDF\Temp\DocConverter\API\input\99638a57dafd\$76D9DDEF7D8D4E7C  
B4DEE6C228977964.docx

Author: PPD

Version Number:

Final 5.0

**CONFIDENTIAL** Version Date:

05SEP2022

Section 6.6) in hSBA titers against *N. meningitidis* serogroups A, C, W, and Y at 1 month after the **second** vaccination for the ABCWY group (Day 31, Month 1), and 1 month after the single dose of MenACWY vaccination for the ACWY group (Day 31, Month 1), relative to baseline (Day 1, Month 0).

The second co-primary immunogenicity variable is the percentages of participants with a 4-fold rise (refer to Section 6.6) in hSBA titers against *N. meningitidis* serogroups A, C, W, and Y at 1 month after the **first** vaccination for the ABCWY group (Day 31, Month 1), and 1 month after the single dose of MenACWY vaccination for the ACWY group (Day 31, Month 1), relative to baseline (Day 1, Month 0).

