C	95%	95%	-10%	0%	99.87%	225
W	95%	95%	-10%	0%	99.87%	225
Y	95%	95%	-10%	0%	99.87%	225
Global Power					99.48%	
Family 2: NI, 2-sided score test (Miettinen and Nurminen, 1985)						
A	95%	91%	-10%	-4%	96.00%	542
C	95%	93%	-10%	-2%	99.95%	542
W	95%	91%	-10%	-4%	96.00%	542
Y	95%	93%	-10%	-2%	99.95%	542
Global Power					91.00%	

n = number of participants; NI = non-inferiority

Considering that approximately 10% of the selected participants might withdraw or not be evaluable for the immunogenicity objectives, the target sample size to be analyzed will be 270 participants per group and 603 participants per group for the first co-primary and the second co-primary objectives, respectively.

Evaluable means all participants included in the set for the statistical analysis defined in Section 9.3. The sample size calculation was performed in PASS 12 (Hintze, 2013). The global power for all 4 strains across Family 1 and Family 2 is the product of individual powers.

Approximately 1206 participants will be randomized in a 1:1 ratio to achieve 1084 evaluable participants (542 per group).

Withdrawals will not be replaced.

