9.4.3 Primary Endpoint(s)

9.4.3.1 Immunological Non-inferiority of MenABCWY vs. MenACWY

Analysis set: The analysis of NI will be based on the PPS.

Statistical method (Family 1): For each of the serogroups A, C, W, and Y, the percentages of participants with 4-fold rise (refer to [Section 9.4.1](#)), and the corresponding exact 2-sided 95% CIs based on Clopper-Pearson method ([Clopper and Pearson, 1934](#)) will be calculated for each study group at 1 month after the second vaccination. The

standardized asymptotic CIs between group differences in percentages will be derived using the method of Miettinen and Nurminen (Miettinen, 1985).

NI criterion: Non-inferiority will be demonstrated if, the lower limit of 2-sided 95% CI for the percent difference in 4-fold rise in hSBA titers ($p1_MenABCWY - p1_MenACWY$) is above -10% , for each serogroup A, C, W, and Y.

Statistical method (Family 2): For each of the serogroups A, C, W, and Y, the percentages of participants with 4-fold rise (refer to Section 9.4.1), and the corresponding exact 2-sided 95% CIs based on Clopper-Pearson method (Clopper and Pearson, 1934) will be calculated for each study group at 1 month after the first vaccination. The standardized asymptotic CIs between group differences in percentages will be derived using the method of Miettinen and Nurminen (Miettinen, 1985).

NI criterion: Non-inferiority will be demonstrated if, the lower limit of 2-sided 95% CI for the percent difference in 4-fold rise in hSBA titers ($p1_MenABCWY - p1_MenACWY$) is above -10% , for each serogroup A, C, W, and Y.

A sensitivity analysis including minimization factors as covariates will be performed using a logistic model and will be detailed in the SAP.

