### 2.5.1. PRIMARY IMMUNOGENICITY ENDPOINT

#### **Immunological non-inferiority: MenABCWY vs. MenACWY (Family 1):**

The first co-primary immunological non-inferiority of the MenABCWY vaccine, compared to MenACWY vaccine, will be demonstrated if the lower limit (LL) of the 2-sided 95% CI for the group difference in percentages of participants in the PPS (as defined in Section 5.5) achieving a 4-fold rise (refer to Section 6.6) in hSBA titers is above -10%, for each serogroup, i.e., the percentages of participants with a 4-fold rise (refer to Section 6.6) in hSBA titers against *N. meningitidis* serogroups A, C, W, and Y at 1 month after the **second** vaccination for the ABCWY group (Day 211, Month 7), and 1 month after the single dose of MenACWY vaccination for the ACWY group (Day 31, Month 1), relative to baseline (Day 1, Month 0).

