#### **Immunological non-inferiority: MenABCWY vs. MenACWY (Family 2):**

The second-co-primary immunological non-inferiority of the MenABCWY vaccine, compared to MenACWY vaccine, will be demonstrated if the lower limit (LL) of the 2-sided 95% CI for the group difference in percentages of participants in the Per Protocol Analysis Set (PPS, as defined in Section 5.5) achieving a 4-fold rise (refer to Section 6.6) in hSBA titers is above -10%, for each serogroup, i.e., the percentages of participants with a 4-fold rise (refer to Section 6.6) in hSBA titers against *N. meningitidis* serogroups A, C, W, and Y at 1 month after the **first** vaccination for the ABCWY group (Day 31, Month 1), and 1 month after the single dose of MenACWY vaccination for the ACWY group (Day 31, Month 1), relative to baseline (Day 1, Month 0).

---

Document: C:\ProgramData\activePDF\Temp\DocConverter\API\input\99638a57dafd\$76D9DDEF7D8D4E7C  
B4DEE6C228977964.docx

Author: PPD

Version Number: Final 5.0

**CONFIDENTIAL** Version Date: 05SEP2022

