**CONFIDENTIAL**

Version Date:

05SEP2022

Where  $p1\_MenABCWY_{(i)}$  denotes the percentages of participants with 4-fold rise (refer to Section 6.6) in hSBA titers for serogroups  $i=A, C, W,$  and  $Y,$  1 month after the **second** vaccination of MenABCWY group and  $p1\_MenACWY_{(i)}$  denotes the percentages of participants with 4-fold rise (refer to Section 6.6) in hSBA titers for serogroups  $i=A, C, W,$  and  $Y,$  1 month after the single vaccination of MenACWY group.

The primary immunogenicity analysis will be performed for the PPS. The primary immunological non-inferiority of the MenABCWY vaccine, compared to MenACWY vaccine, will be demonstrated if the lower limit (LL) of the 2-sided 95% CI for the group difference in percentages of participants achieving a 4-fold rise (refer to Section 6.6) in hSBA titers is above  $-10\%$ , for each serogroup.

For each of the serogroups A, C, W, Y the percentages of participants with 4-fold rise (refer to Section 6.6), and the corresponding exact 2-sided 95% CIs based on Clopper-Pearson method (Clopper and Pearson, 1934) will be calculated for each vaccine group at 1 month post **second** vaccination. The standardized asymptotic CIs between group differences in percentages will be derived using the method of Miettinen and Nurminen (Nurminen, 1985).

Second Co-Primary Immunogenicity Objective (Family 2):

The second co- primary immunogenicity objective is to demonstrate the immunological NI of the antibody response to MenABCWY vaccine, compared to MenACWY vaccine given to healthy participants, previously primed with MenACWY, as measured by percentage of participants with 4-fold rise (refer to Section 6.6) in hSBA titer against each of the *N. meningitidis* serogroups A, C, W, and Y, at 1 month after the **first** MenABCWY vaccination and 1 month after the MenACWY vaccination (single dose). This translates to the following hypotheses:

$$H_0: (p2\_MenABCWY_{(i)} - p2\_MenACWY_{(i)}) \leq -10\%$$

vs.

$$H_1: (p2\_MenABCWY_{(i)} - p2\_MenACWY_{(i)}) > -10\%$$

Where  $p2\_MenABCWY_{(i)}$  denotes the percentages of participants with 4-fold rise (refer to Section 6.6) in hSBA titers for serogroups  $i=A, C, W,$  and  $Y,$  1 month after the **first** vaccination of MenABCWY group

Document: C:\ProgramData\activePDF\Temp\DocConverter\API\input\99638a57dafd\$76D9DDEF7D8D4E7C B4DEE6C228977964.docx

Author: PPD

Version Number: Final 5.0

**CONFIDENTIAL** Version Date: 05SEP2022

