and  $p2\_MenACWY_{(i)}$  denotes the percentages of participants with 4-fold rise (refer to Section 6.6) in hSBA titers for serogroups  $i=A, C, W,$  and  $Y,$  1 month after the single vaccination of MenACWY group.

The secondary immunological non-inferiority of the MenABCWY vaccine, compared to MenACWY vaccine, will be demonstrated if the lower limit (LL) of the 2-sided 95% CI for the group difference in percentages of participants achieving a 4-fold rise (refer to Section 6.6) in hSBA titers is above  $-10\%$ , for each serogroup

For each of the serogroups A, C, W, Y the percentages of participants with 4-fold rise (refer to Section 6.6), and the corresponding exact 2-sided 95% CIs based on Clopper-Pearson method (Clopper, 1934) will be calculated for each vaccine group, at 1 month after the **first** vaccination for the ABCWY group (Day 211, Month 7), and 1 month after the single dose of MenACWY vaccination for the ACWY group (Day 31, Month 1). The standardized asymptotic CIs between group differences in percentages will be derived using the method of Miettinen and Nurminen (Nurminen, 1985). The secondary immunological non-inferiority analysis will be performed for the PPS.

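### SAP 16.1 gives the wrong ABCWY visit day once in each co-primary family, and the Family 1 method sentence puts the control arm at Day 211, where only about 20 control samples are tested

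*SAP*

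**What the plan says.** **Endpoint definitions.** SAP 2.5.1 takes the Family 1 response "at 1 month after the second vaccination for the ABCWY group (Day 211, Month 7") and the Family 2 response "at 1 month after the first vaccination for the ABCWY group (Day 31, Month 1"). In both families the control is taken at Day 31, one month after the single MenACWY dose. The protocol objectives tables (synopsis and section 3.0) agree.

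**SAP 16.1.1, Family 1 variable.** ABCWY is taken "at 1 month after the second vaccination for the ABCWY group (Day 31, Month 1"). The Family 2 variable in the same subsection carries the correct day.

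**SAP 16.1.3, Family 2 method.** ABCWY is taken "at 1 month after the first vaccination for the ABCWY group (Day 211, Month 7").

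**SAP 16.1.3, Family 1 method.** The percentages and their Clopper-Pearson intervals "will be calculated for each vaccine group at 1 month post second vaccination". Protocol 9.4.3.1 has the same rule: "will be calculated for each study group at 1 month after the second vaccination". The hypothesis text just before the SAP sentence instead defines the control proportion as the response "1 month after the single vaccination of MenACWY group".

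**Samples.** Footnote 4 to protocol Table 11 says that A, C, W and Y are tested in all participants at Day 1 and Day 31. At Day 211 they are tested in 250 ABCWY participants and in 20 controls, the latter to protect the blind.

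**The concern.** Section 16.1 is what a programmer works from for both confirmatory tests, and SAP 4.2 sends any interim immunogenicity assessment to 16.1.3 as well. Family 2 may be tested only if Family 1 succeeds, so a wrong visit in Family 1 affects both.

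- **(a) Followed from 16.1.1 alone**, both families use the same Day 31 samples in both arms, and the second-dose hypothesis is never tested.
- **(b) Followed from the Family 2 sentence in 16.1.3 alone**, the first-dose hypothesis is tested on Day 211 ABCWY samples.
- **(c) Followed from the Family 1 method sentence**, ABCWY one month after dose 2 is compared with about 20 controls sampled seven months after MenACWY.

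If the choice between conflicting sentences is made after unblinding, the sponsor would have to show that the data did not drive it.

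**Working it through.** **1. Visit days.** ABCWY is dosed at Day 1 and Day 181. One month after dose 1 is 1 + 30 = Day 31, and one month after dose 2 is 181 + 30 = Day 211. The control arm receives MenACWY at Day 1 and MenB at Days 181 and 211. Its second vaccination is therefore MenB at Day 181, and one month later is Day 211. Protocol Tables 3 and 11 label Visit 4 (Day 211) as the post-vaccination-2 sample for all participants.

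| Place | Dose named | Day given or implied | Day in SAP 2.5.1 |
|---|---|---|---|
| 16.1.1 Family 1, ABCWY | second | 31 | 211 |
| 16.1.1 Family 2, ABCWY | first | 31 | 31 |
| 16.1.3 Family 2, ABCWY | first | 211 | 31 |
| 16.1.3 Family 1 method, ACWY | second (each group) | 211 (implied) | 31 |

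So 2 of the 3 ABCWY day labels are wrong. The control visit in the Family 1 method sentence is also wrong, though there the day is implied rather than printed.

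**2. Sample counts.** Protocol 9.2 plans "270 participants per group and 603 participants per group for the first co-primary and the second co-primary objectives, respectively".

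- Literal (b): 250 ABCWY samples tested at Day 211, against 603 planned: 250/603 = 41%.
- Literal (c): 20 ACWY samples, against 270 planned: 20/270 = 7%. Against the roughly 603 controls tested at Day 31 it is 20/603 = 3%.

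**3. The plan's own power.** Inputs from protocol 9.2: 95% in both groups, n = 225, margin −10%. The two-sided 95% interval corresponds to one-sided 0.025. The Miettinen-Nurminen statistic is

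z = (p̂₁ − p̂₂ + 0.10) / √{[p̃₁(1−p̃₁)/n₁ + p̃₂(1−p̃₂)/n₂] · N/(N−1)},

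where N = n₁ + n₂ and p̃₁, p̃₂ are the maximum-likelihood estimates under a difference of −0.10. Non-inferiority is declared if z > 1.96. Power is the sum of the binomial probabilities over all outcomes that meet this rule.

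- 225 vs 225: 99.48% per serogroup. 225 vs 542: 99.79%. The protocol states 99.87%, so the figure reproduces closely.
- Global, four serogroups taken as independent (as the protocol does): 0.9948⁴ = 97.9% and 0.9979⁴ = 99.2%. The stated 99.48% is 0.9987⁴.

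**4. The literal Family 1 sentence (c).** With 225 ABCWY vs 20 ACWY at 95% vs 95%, power is 91.1% per serogroup and 0.911⁴ = 68.9% global. With 20 × 0.9 = 18 evaluable controls it is 90.2% and 66.1%.

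The documents give no Day 211 control rate, so the rates below are assumptions. Entries are the per-serogroup chance of declaring non-inferiority with 225 vs 20.

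| Assumed Day 211 control rate | ABCWY 95% | ABCWY 85% |
|---|---|---|
| 95% | 91.1% | 3.7% |
| 90% | 96.8% | 17.5% |
| 80% | 99.7% | 59.4% |
| 60% | about 100% | 97.7% |

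An ABCWY rate of 85% lies exactly on the margin against a 95% Day 31 control. The intended design with 225 vs 225 passes there 2.3% of the time. The literal comparison could therefore lose power or be far too lenient, depending on how much the control response has waned.

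**The case against.** The best defence is that the intent is not in doubt. Each wrong day follows a correct dose word. The correct days stand in SAP 2.5.1 and the protocol objectives tables, and the hypotheses in both documents state the right dose for each arm. SAP Table 2 ties Visit 4 to Visit 3, so Day 31 cannot follow dose 2. The slips look like residue from Amendment 2, which exchanged the order of the first-dose and second-dose objectives; 16.1.3 still calls Family 2 secondary. Part (c) is the weakest of the three. The sentence prints no day, it concerns the per-group percentages, and the next sentence, on the between-group interval that decides non-inferiority, gives no time point. The table shells are not available, so nobody can say whether any error reached the programs. The probabilities under (c) describe a reading that nobody intends, at assumed control rates, with evaluable ABCWY counts set against tested control counts.

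Most of this stands, and it limits what can be claimed: no harm has been shown, and the planned sample size is sound. It does not remove the contradictions. The between-group interval in (c) is built from the percentages that the disputed sentence defines, and that sentence is in both documents, so checking the SAP against protocol 9.4.3.1 would not reveal it. A confirmatory specification should not depend on the programmer choosing which section to follow.

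**Conclusion.** The point holds. Two of the three ABCWY day labels in SAP 16.1 are wrong, and the Family 1 method sentence in both documents contradicts the control definition in the hypotheses. This is an internal contradiction, not a complete swap: 16.1.1 has Family 2 right, and 16.1.3 prints no wrong day for Family 1. The planned counts confirm that neither (b) nor (c) is intended.

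Under the intended analysis the stated Family 1 power is unaffected. Under the literal wording of (c), global power at the planning rates falls from 97.9–99.2% to about 66–69%. If the control response has waned by Day 211, the test instead becomes too easy. The direction is unknown, because it rests on assumed Day 211 control rates; the global figures also assume independent serogroups. The correction is needed because these sentences specify the primary analysis, not because a wrong analysis has been shown to be likely.

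**What to change.** - **SAP 16.1.1:** set the Family 1 ABCWY visit to Day 211, Month 7.
- **SAP 16.1.3, Family 2:** set the ABCWY visit to Day 31, Month 1.
- **SAP 16.1.3, Family 1 method:** replace the each-group wording with ABCWY at Day 211 and ACWY at Day 31, and state that the ACWY Day 211 samples enter no primary analysis.
- **Protocol 9.4.3.1:** make the same Family 1 correction at the next amendment. As a minor correction, write the Family 2 criterion with p2 rather than p1.

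The cost is a few lines of SAP wording now. The protocol changes can wait for the next amendment, with whatever ethics committee review it needs. No data, visits or participants are affected.
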